The goal of this pilot study is to determine a meaningful treatment difference in order to conduct a larger confirmatory trial. Given the limited data on treatment responsiveness in COVID-19 populations, we examined various enrollment sizes commensurate with planning a pilot study. Specifically, we undertook a recommended approach for pilot studies in clinical research, which is to not perform hypothesis testing with a significance level set at the traditional value of 0.05.³⁴⁻³⁷ The confidence intervals for the treatment difference were calculated based on demonstrating a reduction in the proportion of subjects needing advanced respiratory support from 0.50 in the placebo group to 0.25 in the sirolimus group. Various levels have been proposed as optimal thresholds for the tolerance of type I error in the context of pilot studies, with the highest being $p=0.25$.³⁴ We chose the type I error rate of 0.2 to denote significant treatment effect between the treatment and placebo arms in our study, as proposed by Stallard.³⁷ A sample size of 30 patients randomized in a 2:1 fashion in favor of sirolimus will allow us to estimate the treatment differences with 80% confidence based on a binomial two-proportion test. A two-sided test will be used since we are unsure if the treatment will have a beneficial effect in this patient population.

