Data Analysis Plan: The primary endpoint of this study is progression to respiratory failure requiring advanced support measures. The difference in proportions of progression between the placebo and sirolimus groups and the 80% confidence interval will be calculated. If the confidence interval for the difference in proportions does not include zero, then we will conclude that the treatment difference is clinically meaningful. Considering the small sample size of our study, the significant impact of age and other pre-existing conditions such as diabetes mellitus on overall prognosis in patients with COVID-19 cannot be accounted for in the primary analysis. Patients will be randomized according to a computer-generated permuted block randomization stratified on age: <50 years, 50 – 64 years, and ≥ 65 years. In case recruitment lags we will add external study sites. In such a scenario, University of Cincinnati and the facilities of the affiliated health systems UC Health, LLC and University of Cincinnati Physicians Company, LLC will follow the same randomization scheme. In case of other external sites, randomization will be stratified based on site in addition to the above-mentioned age-based stratification. As exploratory analysis, we will conduct analyses examining differences based on other prognostic factors and concomitant medications such as corticosteroids, hydroxychloroquine, azithromycin etc. An intent-to-treat analysis will be performed for the primary outcome.

16. Identification and access to source data

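### Age bands used to randomise are left out of the primary analysis, the 80% interval has no named method, and any interval excluding zero is called clinically meaningful in either direction

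*Combined protocol and SAP*

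**What the plan says.** The Data Analysis text is essentially the same in the protocol synopsis, protocol Section 15 and the SAP.

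- Allocation is by "computer-generated permuted block randomization stratified on age: <50 years", with further bands at 50 to 64 and at 65 and over. Block size is not given.
- Primary result: "The difference in proportions of progression between the placebo and sirolimus groups and the 80% confidence interval will be calculated". No interval method is named. The sample-size text refers only to a binomial two-proportion test.
- Age is left out of that analysis. The ground given is "Considering the small sample size of our study"; from this the plan concludes that "the significant impact of age and other pre-existing conditions such as diabetes mellitus on overall prognosis in patients with COVID-19 cannot be accounted for".
- Decision rule: "If the confidence interval for the difference in proportions does not include zero, then we will conclude that the treatment difference is clinically meaningful".
- The level comes from the sample-size text: "We chose the type I error rate of 0.2 to denote significant treatment effect". The test is two-sided because benefit is uncertain.
- If sites are added: "In case of other external sites, randomization will be stratified based on site in addition to the above-mentioned age-based stratification".
- Purpose: "The goal of this pilot study is to determine a meaningful treatment difference in order to conduct a larger confirmatory trial".

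**The concern.** There are three linked faults.

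1. The plan calls age strongly prognostic, builds it into the randomisation, and then says the trial is too small to use it. Three strata and one common risk difference are not too much for 30 patients.
2. With 20 and 10 patients, interval methods differ enough to change both the error rate and, near the boundary, the verdict. If the method is not fixed in advance, it can be settled after the data are seen.
3. The rule treats exclusion of zero as clinical relevance. It gives no direction, no minimum difference and no consequence, although the test is two-sided. The rule speaks of a treatment difference, so it does not call harm a benefit, but a result against sirolimus would carry the same label as one in favour.

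The stake is how the trial is read. The synopsis says phase III trials may be designed from the results, and Section 14.1 rules out an interim look at efficacy, so the end-of-study verdict carries the weight. Patient protection is not at issue, because the DSMB reviews unblinded safety data.

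**Working it through.** **Inputs.** From Section 15: 30 patients at 2:1 (20 sirolimus, 10 placebo), planned rates 0.50 placebo and 0.25 sirolimus, two-sided level 0.2 (z = 1.2816), three age bands. The documents do not give age mix, age-specific risks or block size, so these are assumed below. Differences are sirolimus minus placebo.

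**The plan's own sample size.** No power or half-width is printed. The figure of 30 is reproduced if the criterion (inferred) is that the 80% Wald interval excludes zero at the planned rates:

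n(placebo) = 1.2816² × (0.5×0.5 + 0.25×0.75/2) / 0.25² = 1.6424 × 0.34375 / 0.0625 = 9.03, rounded up to 10, total 30.

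SE = √(0.25×0.75/20 + 0.5×0.5/10) = 0.1854; half-width = 1.2816 × 0.1854 = 0.238.

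Exactly the planned result (5/20 against 5/10) gives −25 points, with Wald interval −48.8 to −1.2 and Miettinen-Nurminen (MN) interval −47.6 to −1.2. The exact chance of excluding zero at the planned rates is 0.562 (Wald), 0.570 (pooled z) or 0.542 (MN). So 80% confidence is the level chosen, not something that 30 patients deliver.

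**Interval method.** All 21 × 11 = 231 possible tables were enumerated, with no age effect.

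| Quantity | Wald | Unstratified MN |
|---|---|---|
| Type I error, common rate 20–60% | 0.233–0.248 | 0.180–0.207 |
| 11/20 vs 3/10 | +1.6 to +48.4 (excludes zero) | −0.2 to +46.1 (does not) |
| 2/20 vs 3/10 | −40.5 to +0.5 (does not) | −42.0 to −1.1 (excludes zero) |

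The two verdicts differ in 14 tables. These carry probability 3.6% at the planned rates, 6.9% at 50% in both arms and 9.7% at 20% in both arms.

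**Decision rule.** Sirolimus 10/20 against placebo 2/10 is 30 points worse (MN +5.5 to +49.3, Wald +8.4 to +51.6) and is labelled clinically meaningful. If sirolimus truly raised the rate from 40% to 50%, 21% (MN) to 26% (Wald) of trials would get the label against sirolimus. With no effect the figure is 9–10% (MN) or 12–16% (Wald), largely the ordinary one-tail share of 0.2. Small observed differences do not pass: the smallest that qualifies is 10 points, in edge tables, or 20 points with 2 to 8 placebo events. By Wald with 3 to 8 placebo events, the smallest qualifying reduction is 25 points.

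**Age bands.** The stratified analysis is the Mantel-Haenszel (MH) risk difference with a stratified MN score interval; a band empty in one arm is merged.

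*No treatment effect:* 24 scenarios of 40,000 trials (age mixes equal, 20/35/45% and 10/30/60%; blocks of 3 or 6; band risks from 50/50/50% to 15/50/85%).

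| Type I error | Stratified MN | Unstratified MN | Wald |
|---|---|---|---|
| All 24 scenarios | 0.199–0.209 | 0.114–0.192 | 0.150–0.234 |
| Steepest risks (15/50/85%) | within the range above | 0.114–0.155 | 0.150–0.184 |

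*Overall rates 50% and 25%, age odds ratio 1 to 4 per band:*

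- Stratified MN excludes zero in 54–61% of trials, with mean half-width 21–23 points and coverage 79–82%.
- Its power is 0.2 to 6.5 points above unstratified MN, and from 1.0 point below to 5.2 points above Wald.
- The stratified and unstratified MN verdicts differ in 2–8.5% of trials.
- Both estimates average a reduction of 24.7 to 25.4 points, so neither is biased.

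The stratified interval must also be specified: an MH interval with the Sato variance covered only 0.75–0.78 in a separate simulation.

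**The case against.** The strongest reply is that the age point is an efficiency preference in a small pilot that states its limitation openly. Stratified randomisation already balances age, and the spread of the estimate hardly changes on adjustment (simulated SD 0.187 against 0.187 for moderate age risks, 0.169 against 0.167 for strong ones). Only the interval width responds. Merging is not rare if ages are skewed: 26–35% of trials at a 10/30/60% mix, and up to 40% with an assumed external site holding a third of patients. Keeping age-only strata when site also joins the randomisation concedes something to sample size. On the rule, a Wald reading with 3 to 8 placebo events already demands the planned 25-point reduction, so trivial benefits do not pass. Wald and MN disagree in only 3.6% of trials at the planned rates.

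Most of this is right, and it limits the size of the point. It does not rescue the claim that age cannot be accounted for. Nor does it supply the missing method: under no effect the two common choices sit on different sides of 0.2 over much of the range. The implicit 25-point threshold depends on a method the plan does not name, and does nothing for results against sirolimus.

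**Conclusion.** The concern holds and should be corrected before unblinding. The missing interval method and the direction-free label rest on the text and exact enumeration, with no assumption about age. Omitting the bands is a lesser fault. It causes no bias and makes an unadjusted interval conservative when age is prognostic, at a cost of up to 6.5 points of power against unstratified MN and close to nothing if age is not prognostic. Those age figures depend on assumed age mix, risks and block size. The small-sample reason remains fair for diabetes and other comorbidities.

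**What to change.** 1. **Primary analysis.** State in the SAP: the primary estimate is the Mantel-Haenszel risk difference (sirolimus minus placebo) stratified by the three randomisation age bands, with a two-sided 80% stratified Miettinen-Nurminen score interval using MH weights; the unstratified Miettinen-Nurminen interval is a sensitivity analysis. An outer band with no patients in one arm is merged into 50–64. If 50–64 then has no patients in one arm, it is merged with the remaining outer band or, if both remain, with the one holding fewer patients (under 50 if equal). If all bands merge, the unstratified interval is used. If external sites join, analysis strata remain age only.
2. **Decision rule.** Replace it with: an interval wholly below zero is a signal of benefit that supports considering a confirmatory trial; an interval wholly above zero is a signal of harm. Clinical relevance is judged separately, by setting the estimate and interval against the planned 25-point reduction and any minimum reduction the investigators name before unblinding. The documents give no minimum.
3. **Sample-size sentence.** Replace the 80% confidence statement with the operating characteristics: at 50% against 25%, an unstratified Wald half-width of about 24 points and a 54–57% exact chance of excluding zero by unstratified methods; for the stratified score interval about 21–23 points and 54–61%, depending on the assumed age effect.

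The cost is SAP wording and a few lines of code, with no extra patients or data. Sparse bands may need merging: under 0.5% of trials with equal bands, 2–5% at 20/35/45%, 26–35% at 10/30/60%. The harm wording would attach to about 9–10% of trials of an inert drug (unstratified MN figure); the change renames those results without making them more frequent. The stated operating characteristics will also look less favourable than the present sentence.

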16.1 Identifying source data

The site PI will keep accurate records to ensure that the conduct of the study is fully documented. Data derived from source documents will be transferred to protocol-specific CRFs. The results of all clinical and clinical laboratory evaluations will be maintained in the participant's medical records or hospital database and the data will be transferred to clinical CRFs, as applicable.

16.2 Updating source documentation

Documents describing the safety profile of an investigational product will be amended as needed to ensure that the description of safety information adequately reflects any new clinical findings. The site PI will provide the IRB with the most up-to-date versions of the above documents as soon as the PI becomes aware of any changes.

16.3 Permitting access to source data

The investigational site participating in this study (University of Cincinnati) will maintain the highest degree of confidentiality for the clinical and research information obtained from the participants in this clinical trial. Medical and research records will be maintained at the study site in the strictest confidence. However, as a part of the quality assurance and legal responsibilities of an investigator, the investigational site will permit the study monitor, authorized representatives of the IRB, the FDA, and health authorities to examine (and when required by applicable law, to copy) clinical records for the purpose of quality assurance reviews, audits, and evaluations of the study safety and progress. Unless required by the laws that permit copying of records, only the coded identity associated with documents or with other participant data may be copied (and all personally identifying information will be removed). Authorized representatives as noted above are bound to maintain the strict confidentiality of medical and research information that is linked to identify individuals.

16.4 Quality control and quality assurance

The PI will keep accurate records to ensure that the conduct of the study is fully documented. The investigator will ensure that all CRFs and participant study files are legible and complete for every participant.

The PI, through the use of the DSMB, will be responsible for the regular review of the conduct of the trial, for verifying adherence to the protocol, and for confirming the completeness, consistency, and accuracy of all documented data and accuracy of source documentation verification.

When the CRFs are complete, they will be reviewed and signed by the PI. All discrepancies identified by the site monitor will be reviewed, and any resulting queries will be resolved with the site PIs and the CRFs will be amended as needed.

17. Ethical considerations and compliance with good clinical practice

17.1 Statement of Compliance

This study was designed to ensure the protection of subjects according to the ethical principles of the Declaration of Helsinki and amendments concerning medical research in human subjects. This clinical study will be conducted using current good clinical practice (cGCP), as delineated in ICH, Guidance for Industry: E6 Good Clinical Practice Consolidated Guidance, and according to the criteria specified in this study protocol. Before study initiation, the protocol and the informed consent documents will be reviewed and approved by the DSMB, the IRB, as well as any other appropriate health authorities. Any amendments to the protocol or to the consent materials will also be approved by the appropriate bodies listed above prior to implementation.

17.2 Informed Consent

Each subject will be provided with oral and written information describing the nature and duration of the study. Written consent must be obtained prior to screening while following the informed consent procedures as detailed in Section 6.3. Prospective participant must be given ample opportunity to review the informed consent and inquire about the results of the study. All participants must read, sign, and date a consent form prior to study participation. Subject will enter the date of the consent. The original, signed consent form will be retained with the study center's records, and each subject will receive a copy. The ICF will provide information about the study to a prospective participant to allow for an informed decision about participation in the study. Consent materials for participants who do not speak or read English will be translated into the participants' appropriate language.

The ICF will be revised and receive IRB approval whenever important new safety information is available, whenever the protocol is amended, and/or whenever any new information becomes available that may affect participation in the trial.

A copy of the ICF will be given to a prospective participant for review. The PI or an approved designee will discuss the consent with the prospective participant and answer questions. The prospective participant will be told that being in the trial is voluntary and that he or she may withdraw from the study at any time, for any reason. The site will document details of the informed consent process within the study records.

18. Privacy and Confidentiality

A participant's privacy and confidentiality will be respected throughout the study. Each participant will be assigned a sequential identification number and these numbers rather than names will be used during collection, storage, and reporting of participant information.

37. Stallard N. Optimal sample sizes for phase II clinical trials and pilot studies. *Stat Med*. 2012;31(11-12):1031-1042.

SCOPE Statistical Analysis Plan

Statistical considerations

Sample size determination: In a study evaluating 201 hospitalized patients with COVID-19 in China, 82% (165 patients) required supplemental oxygen. Among the patients needing supplemental oxygen, 40% (67 patients) progressed to require advanced respiratory support during their hospital stay.⁸ Considering the fact that our study inclusion criteria mandates the need for supplemental oxygen and the presence of at least one additional poor prognostic biomarker, we anticipate that 50% of our control group will progress to require advanced respiratory support during their hospitalization. We expect that treatment with sirolimus will reduce the need for advanced respiratory support to 25%.

The goal of this pilot study is to determine a meaningful treatment difference in order to conduct a larger confirmatory trial. Given the limited data on treatment responsiveness in COVID-19 populations, we examined various enrollment sizes commensurate with planning a pilot study. Specifically, we undertook a recommended approach for pilot studies in clinical research, which is to not perform hypothesis testing with a significance level set at the traditional value of 0.05.³⁴⁻³⁷ The confidence intervals for the treatment difference were calculated based on demonstrating a reduction in the proportion of subjects needing advanced respiratory support from 0.50 in the placebo group to 0.25 in the sirolimus group. Various levels have been proposed as optimal thresholds for the tolerance of type I error in the context of pilot studies, with the highest being $p=0.25$.³⁴ We chose the type I error rate of 0.2 to denote significant treatment effect between the treatment and placebo arms in our study, as proposed by Stallard.³⁷ A sample size of 30 patients randomized in a 2:1 fashion in favor of sirolimus will allow us to estimate the treatment differences with 80% confidence based on a binomial two-proportion test. A two-sided test will be used since we are unsure if the treatment will have a beneficial effect in this patient population.

Data Analysis Plan: The primary endpoint of this study is progression to respiratory failure requiring advanced support measures. The difference in proportions of progression between the placebo and sirolimus groups and the 80% confidence interval will be calculated. If the confidence interval for the difference in proportions does not include zero, then we will conclude that the treatment difference is clinically meaningful. Considering the small sample size of our study, the significant impact of age and other pre-existing conditions such as diabetes mellitus on overall prognosis in patients with COVID-19 cannot be accounted for in the primary analysis. Patients will be randomized according to a computer-generated permuted block randomization stratified on age: <50 years, 50 – 64 years, and ≥ 65 years. In case recruitment lags we will add external study sites. In such a scenario, University of Cincinnati and the facilities of the affiliated health systems UC Health, LLC and University of Cincinnati Physicians Company, LLC will follow the same randomization scheme. In case of other external sites, randomization will be stratified based on site in addition to the above-mentioned age-based stratification. As exploratory analysis, we will conduct analyses examining differences based on other prognostic factors and concomitant medications such as corticosteroids, hydroxychloroquine, azithromycin etc. An intent-to-treat analysis will be performed for the primary outcome.
